5.4.3 Hematologic response

Loss of CHR

Loss of CHR is defined by meeting any of the following:

- WBC count > $20 \times 10^9/L$
- Platelet count $\geq 600 \times 10^9/L$
- Appearance of blasts or promyelocytes in peripheral blood
- Appearance of myelocytes + metamyelocytes $\geq 5\%$ in peripheral blood
- Progressive splenomegaly refractory to therapy (i.e. $\geq 5\text{cm}$ below left intercostal margin)

Loss of CHR must have led to treatment discontinuation because of lack of efficacy (based on the “End of Treatment Phase Disposition” eCRF or “End of Treatment Disposition” eCRF during the Treatment switch phase with Subject status=“lack of efficacy” and Reason of treatment failure = “After start of therapy, loss of CHR, CCyR or PCyR”).

In addition, CML-related death or progression to AP or BC will be considered as loss of CHR in any case (if they occurred on treatment).

Complete hematologic response (CHR)

CHR is defined when all of the following criteria are present at any assessment which is confirmed by another assessment at least after 4 weeks:

- White blood cells (WBC) count < $10 \times 10^9/L$
- Platelet count < $450 \times 10^9/L$

- Basophils < 5%
- No blasts and promyelocytes in peripheral blood
- Myelocytes + metamyelocytes < 5% in peripheral blood
- No evidence of extramedullary disease, including spleen and liver. As extramedullary disease is evaluated less frequently than hematology, the results of these evaluations are carried forward until the next assessment (unless extramedullary disease was not present at the current assessment but present at the next).

The assessment is not considered CHR, if there are any values indicative of CML in AP or BC (i.e. by blasts in bone marrow). The information used for hematological assessment will be obtained from the laboratory, extramedullary and bone marrow data, all merged by patient and date. To accommodate for missing parameters, specific laboratory results may be carried forward up to 14 days such that assessments performed within a two-week period can be combined into one complete evaluation of hematological response. A value will be carried forward for no more than up to the subsequent valid assessment of the respective laboratory parameter. If even after applying this carry-forward algorithm, any of the above laboratory parameters is not available at a given assessment date, the response assessment will be considered missing, unless any of the available values (including those carried forward) indicates that there is no response in which case the assessment will be 'No response'.

For confirmation of CHR, both the initial CHR as well as the confirming assessment (at least 4 weeks after the initial assessment) must satisfy all the criteria mentioned above and no assessment in between indicates 'No response'. The terms "confirmed CHR" and "CHR" are used as synonymous given that the definition of CHR mentioned above already includes a requirement for confirmation.

5.4.4 Treatment Failure

The following events will constitute 'treatment failure', and are based on the ELN criteria ([Baccarani et al 2013](#)) defining failure of a second line treatment adapted to include discontinuation of randomized treatment as an event:

- No CHR or > 95% Ph+ metaphases at three months after initiation of therapy or thereafter
- BCR-ABL1 ratio > 10% IS and/or > 65% Ph+ metaphases at six months after initiation of therapy or thereafter
- BCR-ABL1 ratio > 10% IS and/or > 35% Ph+ metaphases at 12 months after initiation of therapy or thereafter
- Loss of CHR, CCyR or PCyR at any time after initiation of therapy
- Detection of new BCR-ABL1 mutations which potentially cause resistance to study treatment (T315I and V299L), at any time after initiation of therapy
- Confirmed loss of MMR in 2 consecutive tests
- New clonal chromosome abnormalities in Ph+ cells: CCA/Ph+: at any time after initiation of therapy

- Discontinuation from randomized treatment for any reason* (Note that Reason for treatment discontinuation="completed" doesn't indicate a premature treatment discontinuation)

5.4.5 CML progression to accelerated phase (AP) or blast crisis (BC)

For the evaluation of CML progression to AP or BC, the following criteria will be used. Accelerated phase (AP) is defined by any of the following:

- $\geq 15\%$ blasts in the peripheral blood or bone marrow aspirate, but $< 30\%$ blasts in both the peripheral blood and bone marrow aspirate
- $\geq 30\%$ blasts plus promyelocytes in peripheral blood or bone marrow aspirate, but $< 30\%$ blasts in both the peripheral blood and bone marrow aspirate
- $\geq 20\%$ basophils in the peripheral blood
- Thrombocytopenia ($< 100 \times 10^9/L$) that is unrelated to therapy*

*As thrombocytopenia is a known adverse reaction to CML therapy, platelets $< 100 \times 10^9/L$ are only considered as CML-AP if the patient had these values within 30 days of treatment discontinuation due to disease progression. In this case, comments are to be provided on the termination page that thrombocytopenia is indicative of progression to AP and an adverse event (AE) entered with relationship to study treatment = 'Not suspected'

Blast crisis (BC) is defined by any of the following:

- $\geq 30\%$ blasts in peripheral blood or bone marrow aspirate
- Appearance of extramedullary involvement other than hepatosplenomegaly proven by biopsy (i.e., chloroma).
The second bullet criteria can't be considered in this study as this information was not collected.

5.4.6 CML-related deaths

CML-related death is considered as any death during treatment or follow-up (safety or survival)

- if the principal cause of death is marked as "study indication" in the eCRF by the investigator,
- or if the death occurred subsequent to documented progression to AP/BC and the cause of death is reported as "unknown" or not reported by the investigator.

With respect to the second bullet, as "unknown" cause of death will be coded to the Medical Dictionary for Regulatory Activities (MedDRA) preferred term 'Death', this MedDRA coding will be used in the derivation of CML-related death.

5.4.7 Disease progression

The following events are considered disease progression

- CML-related deaths
- Accelerated phase (AP)
- Blast crisis (BC)

5.4.8 Overall survival

This includes all-cause deaths.

5.5 Derivation of response rates and categories

5.5.1 Response rate at a specific time point

The molecular and cytogenetic response evaluations will be summarized by the following mutually exclusive categories which are based on the respective assessment within the time window:

- **Response categories** (sections 5.4.1 and 5.4.2): Patients with an available assessment at that time point (+/- time window) indicating any of the response categories.
- **No response:** Patients with assessment at that time point (+/- time window) indicating 'no response'
- **Missing:** Patients without an evaluable response assessment at that time point (+/- time window). This category is then further split into patients who are ongoing without treatment failure at the beginning of the relevant time window, patients who are ongoing with treatment failure at the beginning of the relevant time window, patients who discontinued due to lack of efficacy, disease progression (PD) or death and patients who discontinued due to other reasons.

5.5.2 Response rate by a specific time point (best response)

In this analysis, patients who had achieved any response at or before the time point will be displayed in their best response category, no matter if they lost the response/discontinued or not. Therefore this response rate represents the best observed response rate up to that specific time point (including the time window).

Patients for whom an evaluable response assessment was never provided will be classified as 'Missing'.

5.6 Statistical models

5.6.1 Primary analysis

The null hypothesis of equality of MMR rate at 24 weeks in the two treatment arms will be tested against two-sided alternative. The statistical hypotheses are:

$$H_0: RA_{24wk} = RB_{24wk} \text{ versus } H_A: RA_{24wk} \neq RB_{24wk}, \text{ for a two-sided test}$$

where RA_{24wk} is the probability of MMR rate at 24 weeks in asciminib arm and RB_{24wk} is the probability of MMR rate at 24 weeks in bosutinib arm.

The Cochran-Mantel-Haenszel chi-square test X^2_{CMH} (implemented via SAS procedure FREQ with CMH option in the TABLES statement), stratified by the randomization stratification factor, i.e. cytogenetic response status (MCyR vs no MCyR) at screening, will be used to test the difference in response rates between the treatment arms. The p-value corresponding to the CMH test for "general association" will be used which follows a Chi-square distribution with one degree of freedom.

The 95% confidence interval for the unstratified difference in MMR rate at 24 weeks between treatment groups will be provided using the Wald method (implemented via SAS procedure `FREQ` with `RISKDIFF` option in the `TABLES` statement, under the default `METHOD=WALD` and `VAR=SAMPLE`). If the 2×2 table is with asciminib in row 1, bosutinib in row 2, MMR in column 1 and No MMR in column 2, then the SAS output will give the estimate of (risk for MMR at 24 weeks in asciminib – risk for MMR at 24 weeks in bosutinib). The corresponding Mantel-Haenszel estimate of common risk difference and 95% confidence interval will also be presented (with `RISKDIFF(COMMON)` option in the `TABLES` statement, taking the Mantel-Haenszel estimate from the SAS output table).

If the sampling assumptions for chi-square test is not met (i.e. the expected frequencies should exceed 5 for all of table cells), the exact Cochran-Mantel-Haenszel test will be used (implemented via SAS procedure `MULTTEST`). The test is performed by running a stratified version of the Cochran-Armitage permutation test [Armitage et al. 1969]. In studies with stratified randomization, the chi-square approximation is considered appropriate for the X^2_{CMH} statistics if the rule of Mantel and Fleiss [Mantel and Fleiss 1980] is satisfied.

Confidence interval for MMR rate within each treatment arm

MMR will be summarized in terms of percentage rates with 95% confidence interval using exact binomial confidence interval (implemented using SAS procedure `FREQ` with `EXACT` statement for one-way table [Clopper and Pearson 1934]).

5.6.2 Key secondary analysis

The null hypothesis of equality of MMR rate at 96 weeks in the two treatment arms will be tested against two-sided alternative. The statistical hypotheses are:

$$H_0: RA_{96wk} = RB_{96wk} \text{ versus } H_A: RA_{96wk} \neq RB_{96wk}, \text{ for a two-sided test}$$

where RA_{96wk} is the probability of MMR rate at 96 weeks in asciminib arm and RB_{96wk} is the probability of MMR rate at 96 weeks in bosutinib arm.

The same approaches as for the primary endpoint (Section 5.5.1) will be applied here for the Cochran-Mantel-Haenszel chi-square test X^2_{CMH} , the 95% Wald confidence interval for the difference in MMR rate at 96 weeks between treatment groups, the Mantel-Haenszel estimate of common risk difference with 95% confidence interval, and the confidence interval for MMR rate within each treatment arm.

Multiplicity adjustment

Formal statistical testing of the key secondary endpoint will be performed with $\alpha = 0.05$ (two-sided) only if the primary endpoint is significant by means of a gatekeeping procedure to control the overall alpha level.

5.6.3 Other analyses

Mantel-Haenszel common odds ratio

To obtain Mantel-Haenszel estimates of the common odds ratio and the corresponding 95% confidence interval in exploratory analyses, it requires SAS procedure FREQ with CMH and RELRISK options in the TABLES statement.

Logistic Regression

Odds ratio will be used as a measure of association between treatment and response in exploratory analyses ([Section 2.14](#)). The odds ratio will be derived from the logistic regression model (implemented using SAS procedure LOGISTIC, with treatment specified as an explanatory variable in the CLASS statement) which allows for including not only the stratification factor but also for adjustments for other covariates (both categorical and continuous). The odds ratio will be presented with 95% Wald confidence limits.

In cases where an exact test has been used to compare response rates, the odds ratio should be determined using exact logistic regression, and the odds ratio presented with exact 95% confidence limits. In these cases, SAS PROC LOGISTIC with EXACTONLY option will be used.

Kaplan-Meier estimates

An estimate of the survival function in each treatment group will be constructed using Kaplan-Meier (product-limit) method as implemented in PROC LIFETEST with METHOD=KM option. The PROC LIFETEST statement will use the option CONFTYPE=LOGLOG.

Median survival for each treatment group will be obtained along with 95% confidence intervals calculated from PROC LIFETEST output using the method of [\[Brookmeyer and Crowley 1982\]](#). Kaplan-Meier estimates of the survival function with 95% confidence intervals at specific time points will be summarized. The standard error of the Kaplan-Meier estimate will be calculated using Greenwood's formula [\[Collett 1994\]](#).

Hazard ratio

Hazard ratio will be estimated by fitting the Cox proportional hazards model using SAS procedure PHREG (with TIES=EXACT option in the MODEL statement).

A stratified unadjusted Cox model will be, i.e. the MODEL statement will include the treatment group variable as the only covariate and the STRATA statement will include stratification variable(s). Hazard ratio with two-sided 95% confidence interval will be based on Wald test.

Cumulative incidence

The cumulative incidence proportion (CIP) will be estimated using SAS procedure LIFETEST or PHREG with EVENTCODE=Code for event of interest (e.g. MMR) as option in the MODEL statement, whereas code=0 for censored subjects and any other code (e.g. code=2) for subjects who dropped out due to a competing risk. The estimated CIP at the defined time points will be presented with 95% CI together with number of subjects with events, number of subjects with competing risks, and number of subjects censored.

5.6.4 Calculation of exposure-adjusted incidence rate

To adjust for different durations of exposure across treatment arms, the incidence rate per 100 patient-years of exposure (exposure-adjusted incidence rates of adverse events) will be calculated.

The IR/100 pyr is defined as numerator/denominator, where

- Numerator = number of patients with the adverse events of interest (not the number of events; one patient may have more than one event).
- Denominator = patient-years = total time at risk in years = among all patients in the population, sum of the duration of exposure (in days) until the first onset of the event of interest, if the patient experienced the event, or until the date of last dose if the patient did not experience the event / 365.25.

The patient-years (i.e. total time at risk in years) will be calculated as the sum of times at risk in days over all patients in the population / 365.25.

The time at risk for a patient in days will be calculated as follows:

- If the patient experienced the event of interest, the time at risk for this patient is the duration of exposure from the first dose of treatment until the first onset of the event.
- For patients without an event of interest, the time at risk is the total duration of exposure during core study, as applicable.

6 Reference

1. Armitage P, McPherson CK and Rowe BC (1969). Repeated significance tests on accumulating data. *J. R. Statist. Soc. A*, 132, 232-244.
3. Branford S, Hughes T (2006) Diagnosis and monitoring of chronic myeloid leukemia by qualitative and quantitative RT-PCR. *Methods Mol Med*; 125:69-92.
4. Brookmeyer R and Crowley J (1982). A Confidence Interval for the Median Survival Time. *Biometrics*, 38, 29 - 41.
5. Clopper CJ and Pearson ES (1934). The use of confidence or fiducial limits illustrated in the case of the binomial. *Biometrical*, 26, 404-413.
6. Collet D (1994). Modelling survival data in medical research. London, Chapman & Hall.

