2. **on-treatment period:** from date of first administration of study treatment to 30 days after date of last actual administration of study treatment (including start and stop date) (LD). Note: Patients will be treated up to the end of study treatment period (EOsT). This will be the last actual administration of study treatment for each patient if the patient has not discontinued study treatment earlier. On this date, all patients without treatment switching will have been treated for at least 96 weeks unless patients have discontinued study treatment earlier. After this period, the assigned study treatment will be made available, may be outside of this study, to patients who in the opinion of the investigators are still deriving clinical benefit.
3. **post-treatment period:** starting at day 31 after last administration of study treatment.

For subjects with treatment switching from bosutinib to asciminib:

- **pre-treatment period:** from day of patient's informed consent to the day before first administration of study treatment (FD)
- **on-treatment period:** from date of first administration of study treatment to either the day before the first administration of asciminib (FD_{switch}) or 30 days after the date of last actual administration of bosutinib (LD), whichever comes first.
- **post-treatment period:** from day 31 after last administration of bosutinib to the day before the first administration of asciminib (FD_{switch}). If the end date is before the start date, this period is not applicable.
- **on-switched treatment period:** from date of first administration of asciminib (FD_{switch}) to 30 days after date of last actual administration of asciminib (LD_{switch}).
NOTE: Subjects are treated in the study up to end of study treatment period (EOsT). On this date, all subjects with treatment switching will have been treated for at least 48 weeks after switching unless they have discontinued the switched treatment earlier.
- **Post-switched treatment period:** from day 31 after last actual administration of asciminib (LD_{switch}).

If dates are incomplete in a way that clear assignment to pre-, on-, post-, on-switched-, post-switched-treatment period cannot be made, then the respective data will be assigned to the on-treatment period.

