2.8.1 Adverse events (AEs)

AE summaries will include all AEs occurring during the on-treatment period (or the on-switched treatment period). All AEs collected in the AE eCRF page will be listed along with the information collected on those AEs e.g. AE relationship to study drug, AE outcome, etc. AEs with start date outside of the on-treatment period will be flagged in the listings.

AEs will be summarized by number and percentage of subjects having at least one AE, having at least one AE in each primary system organ class (SOC) and for each preferred term (PT) using MedDRA coding. A subject with multiple occurrences of an AE will be counted only once in the respective AE category. A subject with multiple CTCAE grades or the same preferred term will be summarized under the maximum CTCAE grade recorded for the event. AE with missing CTCAE grade will be included in the 'All grades' column of the summary tables.

In AE summaries, the primary system organ class will be presented alphabetically and the preferred terms will be sorted within primary SOC in descending frequency. The sorting order for the preferred term will be based on their frequency in the asciminib arm.

The following adverse event summaries will be produced by treatment arm for the Safety set and Switch Analysis Set: overview of adverse events and deaths, AEs by SOC and PT, summarized by relationship, seriousness, leading to treatment discontinuation, leading to dose interruption/adjustment, requiring additional therapy, and leading to fatal outcome. The study treatment-related AEs/SAEs/AEs leading to treatment discontinuation as well as SAE with fatal outcome are summarized for the Safety set and Switch Analysis set.

For posting to ClinTrial.gov and EudraCT, a summary table of on-treatment deaths and serious AEs and another summary table of non serious AEs by treatment, both including occurrences (an occurrence is defined as >1 day between start and prior end date of record of same preferred term) and sorted by SOC and PT, will be presented as well.

In order to account for differences in exposure between the treatment arms, incidence rates of AEs and SAEs will be presented by adjusting for duration of treatment period in patient-years. They will also be reported by time intervals (i.e. period of emergence: the event is assigned to the interval when it first started): 0 to 2 months, > 2 months to 6 months, > 6 months to 12 months, >12 months and more after the start of study treatment.

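### SAP Section 5.6.4 leaves the factor of 100 out of its rate per 100 patient-years and counts adverse events over a window up to 30 days longer than the time at risk

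*Combined protocol and SAP*

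**What the plan says.** The section introduces "the incidence rate per 100 patient-years of exposure" and then gives the formula: "The IR/100 pyr is defined as numerator/denominator, where" the two parts are:

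- "Numerator = number of patients with the adverse events of interest", counting patients rather than events;
- "Denominator = patient-years = total time at risk in years", summed to first onset for patients with the event, and otherwise "until the date of last dose if the patient did not experience the event / 365.25".

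It repeats the rule for event-free patients: "For patients without an event of interest, the time at risk is the total duration of exposure during core study, as applicable". Section 2.4.1 defines duration of exposure as last dose minus first dose plus one day, so nothing after the last dose is included.

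Section 5.6.4 gives no window of its own for the events in the numerator. The general rule is in Section 2.8.1: "AE summaries will include all AEs occurring during the on-treatment period (or the on-switched treatment period"). For patients who do not switch, Section 2.1.1 defines the on-treatment period as "from date of first administration of study treatment to 30 days after date of last actual administration of study treatment". For bosutinib patients who switch, it ends at that point or on the day before the first asciminib dose, whichever is earlier.

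Section 2.8.1 describes the same rates as adjusted for the length of the treatment period, which is not the exposure time used in Section 5.6.4. Both SAP versions that contain Section 5.6.4 carry the same wording.

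**The concern.** There are two separate inconsistencies.

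**Scale.** Patients divided by patient-years is a rate per one patient-year. Programmed literally under a per-100 label, the printed value is 100 times too small.

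**Window.** An event-free patient who has stopped drug is still watched for up to 30 days, during which an event would put that patient in the numerator. Those days are missing from the denominator. The rate is then too high, by an amount that depends on how long patients were exposed. Section 5.6.4 says that the calculation exists to adjust for different exposure between arms, so an error that itself varies with exposure works against that purpose. At stake is how a reader compares adverse event and serious adverse event rates between asciminib and bosutinib.

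**Working it through.** The plan states no numerical rate here, so there is no figure to reproduce.

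**Inputs from the SAP.** Tail w = 30 days (2.1.1). Event-free time ends at last dose (5.6.4). Year = 365.25 days.

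**Assumed, because the documents do not give them.** Constant hazard L per year, the same on drug and in the tail; exposure T of 12 to 96 weeks; and discontinuation and switching patterns.

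**Scale.** With L = 0.20 and matched windows, the formula as written returns 0.20. The labelled unit requires 100 x 0.20 = 20.0. The factor is the same in both arms.

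**Window, everyone with a full tail.** Let S = exp(-L(T + w)). A fraction 1 - S has the event. Mean time at risk over the full window is (1 - S)/L, and the plan drops w for each event-free patient, so

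rate as written = (1 - S) / [(1 - S)/L - wS]

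inflation = 1 / [1 - LwS/(1 - S)], roughly 1 + w/T for rare events.

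With L = 0.20 and Lw = 0.20 x 30/365.25 = 0.01643:

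- T = 168 days: S = exp(-0.20 x 198/365.25) = 0.897; LwS/(1 - S) = 0.1434; inflation 1/(1 - 0.1434) = 1.168.
- T = 672 days: S = exp(-0.20 x 702/365.25) = 0.681; LwS/(1 - S) = 0.0350; inflation 1/(1 - 0.0350) = 1.036.

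Inflation over the range of assumptions:

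| Hazard per year | 12 weeks | 24 weeks | 48 weeks | 96 weeks |
|---|---|---|---|---|
| 0.05 | 1.353 | 1.176 | 1.087 | 1.042 |
| 0.20 | 1.342 | 1.168 | 1.080 | 1.036 |
| 1.0 | 1.289 | 1.129 | 1.050 | 1.014 |
| 3.0 | 1.189 | 1.064 | 1.013 | 1.001 |

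A simulation of 400,000 patients per case at hazard 0.20 agrees. The rule as written gave 0.233 per patient-year at 24 weeks and 0.207 at 96 weeks; matched windows gave 0.199 and 0.200.

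**Between arms, equal true hazard 0.20.**

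- 24 against 96 weeks, full tails: 1.1675/1.0363 = 1.13.
- Mixed case: in one arm 20% stop at 12 weeks, in the other 50%; everyone else is ongoing at a 48-week cut-off and so has no tail. Inflation is 1.022 and 1.072, ratio 1.05.
- Same case, half of the stoppers in the second arm switching without a gap, so with no tail: 1.036/1.022 = 1.01.
- Same case, all of them switching without a gap: 1.000/1.022 = 0.98.

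**If the hazard falls to zero after last dose.** No events arise in the tail, so the rule as written recovers the on-drug rate. A denominator extended by 30 days would then dilute it by 1/[1 + LwS0/(1 - S0)], with S0 = exp(-LT). At L = 0.20 this is 1/(1 + 0.1705) = 0.854 at 24 weeks and 1/(1 + 0.0369) = 0.964 at 96 weeks, a ratio of 0.854/0.964 = 0.89.

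**The case against.** The best defence is that the practical consequence is small. The unit is stated correctly in words, so a programmer would probably supply the 100, and its absence cannot affect a comparison. The plan specifies no rate ratio, confidence interval or test for these rates. Section 2.8.1 also reports crude percentages and incidence by period of emergence, neither of which uses this denominator. All of this stands, and it limits the importance of the point. It does not reconcile the two windows, and no other section does so.

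Three stronger readings are tempting but not supported.

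- A reader might infer that the rule necessarily inflates the bosutinib rate relative to asciminib. The documents shown give no exposure, discontinuation or switching by arm. Only bosutinib patients can switch, their tail is cut at the first asciminib dose, and Section 2.1.1 counts bridging bosutinib in the last-dose date. A bridged switcher may have almost no tail, which can remove or reverse the effect.
- A reader might infer that only patients who discontinue early have a tail. That fits the 24- and 96-week cut-offs. The end-of-study-treatment cut-off is 30 days after treatment ends for the study (Section 2.1), so patients treated to that date have one too.
- A reader might infer that extending the denominator by 30 days is simply the correct answer. That returns the true rate only if the hazard continues unchanged after last dose. Where events subside off drug, it dilutes the on-drug rate, and more so in the arm with shorter exposure.

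**Conclusion.** The section is wrong as written on both counts. The missing 100 is a slip of scale with no effect on the comparison. The window mismatch biases the rate upward whenever events arise in the tail. For rare events with full tails the bias is roughly 30 days divided by mean exposure: about 17% at 24 weeks and 4% at 96 weeks at hazard 0.20 per year. It fades for common early events once exposure is long enough for most patients to have had the event.

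The mismatch itself follows from the text and needs no assumption. Its effect between arms does. Under equal hazards the spurious ratio ranged from 1.13, through about 1.00, to 0.98 as more bosutinib stoppers switch without a gap, and it also depends on the off-drug hazard. The rates are descriptive safety output and no formal test is affected. The correction is worth making because it is cheap and the rates exist to support an exposure-adjusted comparison.

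**What to change.** In Section 5.6.4, define the rate as 100 x (patients with the event) / patient-years, and state one window that governs both parts. Either of these is consistent:

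1. Keep the Section 2.1.1 on-treatment period for events, and end time at risk at the earliest of first onset, the end of that period (including the cut at the day before the first asciminib dose), death and data cut-off.
2. Keep the last-dose denominator, and count only events with onset up to last dose.

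The first describes risk on and shortly after treatment, the second risk on drug. The SAP should say which is intended. It should also state how time is counted when a first onset falls after last dose: reading that time as capped at last dose changes the 24-week inflation at hazard 0.20 only from 1.168 to 1.169. Apply the same rule to the on-switched period, and align the description in Section 2.8.1.

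The cost is a sentence or two of SAP text, one derived variable, and a rerun of any rate tables already produced under the present wording. No data collection changes.
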